### **Cardiopulmonary exercise testing:**

As the metabolic response to exercise indirectly reflect mitochondrial function, metabolic exercise testing will be conducted with 12-lead EKG monitoring after an overnight fast at baseline and at the end of 12 weeks of NR administration. Cardiopulmonary exercise testing will be performed using a ramp protocol while wearing a facemask enabling breath-by-breath analysis of inspired and expired air (SensorMedics, CA) as performed previously in our laboratory. EKGs are obtained at rest, after each minute of exercise, at end-exercise, and at each minute for 5 minutes after exercise. Blood pressure will be measured at rest, at the end of each stage of exercise (3 minutes in duration), at end-exercise, and at 3 minutes after exercise. Exercise will be symptom-limited (fatigue, shortness of breath or chest pain) and supervised by an experienced nurse and a LIP investigator of this study. Exercise will be terminated prior to this end-point if evidence of severe ischemia is noted ( $>2$  mm ST segment depression in leads with isoelectric segments at rest, hypotension, ventricular tachycardia) or if the patient wishes to stop exercise. For patients with interpretable EKGs (absence of significant resting ST-T wave or major conduction abnormalities), EKG criteria for ischemia is  $\geq 1$  mm ST segment depression with a horizontal or down-sloping configuration in at least 2 contiguous leads. Analysis of  $\text{VO}_{2\text{max}}$  and the anaerobic threshold will be measured and compared to each subject at baseline and after completion of the NR supplementation protocol. Subjects will be asked not to significantly modify activity levels for the duration of the 16-week study.

### **Echocardiography:**

All patients will undergo baseline resting echocardiography (optional at Visit 1 if PI feels there is an adequate and timely historical echo) and follow up echocardiography at 12 weeks. All studies will be performed at Walter Reed National Military Medical Center or the NIH Clinical Center. Two dimensional and three dimensional images may be acquired in real time through standard imaging acquisition techniques.

Parasternal long axis (2D) will be utilized to measure left ventricular chamber size at end systole and end diastolic, intraventricular and posterior left ventricular wall thickness, left ventricular outflow tract, aortic root, and ascending aorta size, and the morphological integrity of the mitral and aortic valve. Color Doppler will assess for mitral regurgitation and aortic regurgitation. The size and function of the right ventricle and the morphology of the tricuspid valve will be assessed through the parasternal long axis right ventricular inflow views. Color Doppler will assess for

tricuspid regurgitation and a continuous flow Doppler interrogation through the tricuspid valve will estimate pulmonary arterial systolic pressure.

Parasternal short axis (2D) images will be acquired to assess regional wall motion of the left ventricular starting first at the apex then proceeding cranially to include the mid ventricle and finally the base. At the base of the heart, 2D imaging will assess the morphology and function of the aortic, tricuspid and pulmonic valve. Color doppler interrogation of the three valves will assess for regurgitation. Continuous wave doppler through the tricuspid valve will estimate pulmonary arterial systolic pressure. Continuous wave doppler through the pulmonic valve will be used to assess for pulmonic stenosis.

A thorough interrogation of the left ventricle will be obtained through the apical four chamber view (2D). Left ventricular cavity size, wall thickness (inferoseptum and anterolateral walls), and end diastolic area and volume will be measured. Left and right atrial areas and volumes will also be measured in the apical four chamber view. Color doppler will assess the presence and degree of mitral and tricuspid regurgitation. Tissue doppler interrogation of the left ventricle will assess for left ventricular filling pressures. Pulse wave doppler interrogation of the mitral valve inflows will be recorded and, in conjunction with the tissue doppler data set, be employed to assess diastolic function. Apical two chambers views will be utilized to assess overall left ventricular systolic function as well as regional wall motion of the anterior and lateral walls. Color Doppler will be used to assess the function of the mitral valve in the apical two chamber view. After completion of two dimensional imaging, 3D echocardiography data sets may be obtained in the apical two and four chamber views.

Finally, subcostal images will be obtained. This dataset will provide information on the presence and size of a pericardial effusion, overall left and right ventricular size and systolic function as well as the degree of tricuspid and mitral regurgitation as assessed by color Doppler.

### **Metabolomic analysis:**

Recently, the combined use of exercise testing and metabolomics have been used to uncover metabolic disturbances in diabetic subjects. At the same time, metabolomics have identified that impediments in metabolic pathways prevent the full catabolism of fuel sources with worsening heart failure and that left ventricular assist device placement to unload the heart reverses accumulation of these metabolic intermediates. Combining these concepts we plan to undertake metabolomic analysis of heart failure subjects at baseline and in response to NR both at rest and within 3 minutes of cessation exercise at the time of the CPET testing. Serum samples will be collected at the NIH for shipping to the metabolomics core at the UW (<http://depts.washington.edu/nwmrc/>). LC-MS will be performed on serum samples using an

Agilent LC-AB Sciex 5500 QQQ MS instrument to assess the relative abundance of  $\approx$  200 aqueous metabolites. In addition MTBSTFA derivation will be employed to extract polar compounds to measure TCA, glycolysis, amino acid and fatty acid intermediates by GC-MS using the Agilent GC-5975C MSD instrument. Analytes at baseline and in response to CPET will be compared pre- and post- NR supplementation and the data will be interrogated by the NHLBI Bioinformatics Core facility.

### **Cytokine profiling:**

Circulating cytokine levels have been found to directly correlate with worsening functional capacity in heart failure patients and have been shown to have prognostic value as a biomarker. Emerging evidence additionally supports that exercise training and NR reduce cytokine production. Taken together, we would propose that NR supplementation may similarly reduce circulating cytokine production. To investigate this, serum samples from subjects will be collected at baseline and in response to peak exercise during the CPET procedure pre- and post-NR supplementation. Cytokine, chemokine and acute phase reactants will be quantified using the Luminex bead based multiplexing assay to measure  $\approx$  40 analytes simultaneously using the NIH Center for Human Immunology standardized protocols.

### **Skin biopsy:**

A recent study has shown that human primary fibroblasts incubated with serum from individuals, pre- and post-exercise, showed an upregulation of mitochondrial regulatory genes following exercise. We will employ this same approach using serum obtained from study subjects pre- and post NR administration. A single 3mm or less skin biopsy sample would be obtained at the beginning of the study. The assessment of mitochondrial oxidative phosphorylation in primary skin fibroblasts conditioned with serum from heart failure subjects pre- and post-NR would validate and augment the data acquired by NRM spectroscopy.

## **6. Dietary Supplement:**

Niagen™ is a commercially-available form of nicotinamide riboside (NR). The nucleoside NR is a single chemical moiety containing nicotinamide and ribose. NR is a form of vitamin B3 present in trace amounts in foods like milk, yeast extract and beer. It is also postulated that NR is generated in the gastrointestinal tract as part of dietary NAD+ digestion. Thus, humans are constantly exposed to NR from the diet, albeit at low levels. Since 2013, Niagen™ has been sold as a dietary supplement in the United States. Labeling guidelines recommend consumers to limit their intake to 2 capsules/day, which amounts to 250 mg/day. This recommended level is the

equivalent of 3.8 mg/kg bw/day, which is 1000-fold less than the highest dose determined to be safe and well tolerated in rats, and a quarter of the dose proposed for this pilot clinical trial.

There is no limit on the duration of ingestion. Limited animal model and human data exist on the pharmacokinetics and safety of orally administered NR. However, ChromaDex has conducted a recent randomized, double-blind, cross-over, pharmacokinetic study (14NBHC, unpublished results) which demonstrated that NR was readily absorbed and detectable in human plasma, white blood cells, and urine. In addition, NR was well tolerated and presented no toxicity following a single dose up to 1000 mg in human subjects . Moreover, in an acute toxicology study, rats that were given a single oral dose (5000 mg/kg) of NR did not show clinical signs of toxicity or mortality (unpublished results).

Niacin is a form of vitamin B3 and has been used for a long time treat hypercholesterolemia and pellagra. Niacin administration can lead to undesirable effects, such as spontaneous flushing. Studies in animal models suggest that flushing results from nicotinic acid-mediated activation of the G-coupled receptor, GPR109A. NR has low affinity for GPR109A, and experiments in cell lines expressing GPR109A demonstrate that nicotinic acid, but not NR, activates the receptor. Thus, based on these findings, oral ingestion of NR may not result the spontaneous flushing that has been associated with high doses of niacin administration.

**Route of administration:** oral

**Dosing instructions:** BID dosing starting at 250 mg bid with incremental uptitration to 1000 mg bid over the course of the study.

**Supply:** Supplement will be supplied by ChromaDex

**Manufactured by:** W.R. Grace & Co. [name],  
USA

**Toxicology:** None known.

**Drug Interactions:** None known.

**Off-label use:** Considering the clinical investigation is designed to study the relationship between a dietary supplement's effect on structure or function in humans or to characterize the mechanism by which a dietary supplement acts to maintain such structure or function this study would not need to be conducted under an IND. Under the Dietary Supplement Health and Education Act of 1994, a dietary supplement is not considered a drug and is not subject to the premarket approval requirements for drugs if the intended use for which it is marketed is only to affect the structure or any function of the body (i.e., not intended to be used for a therapeutic purpose). Similarly, whether an IND is needed for a clinical investigation evaluating a dietary supplement is determined by the intent of the clinical investigation. If the clinical investigation is intended only to evaluate the dietary supplement's effect on the structure or function of the body, an IND is **not** required.

## **7. Data and Biospecimen Management Plan**

### **Data Management and Access at the NIH:**

Primary research data will be coded by replacing individually identifying information (such as name) with a code that will enable the investigator to readily ascertain the identity of the subject through the use of a code-key, but will not reveal the identity of subjects to parties not authorized to have access to individual subject identifiers.

**Data Management/Monitoring and Access at participating sites:**

Paper case report forms (CRF) will be generated by the clinical team at WRNMMC for visits which take place there and information will be entered into an NHLBI-approved database selected by the NIH team. CRFs related to study visits conducted at the WRNMMC heart failure clinic will be completed and kept by the WRNMMC study team. Coded medical records generated at WRNMMC may be shared with the NIH team to confirm compliance with the protocol. CRFs related to NIH study visits will be completed and kept by [name] or his designee in an NHLBI-approved database. Monitoring will be done according to NHLBI Office of the Clinical Director schedule.

**Biospecimen Management at the NIH:**

Samples will be de-identified prior to storage on the 5th floor of building 10 in laboratory for the principal investigator following current NIH sample storage guidelines. Samples and data will be stored, using codes assigned by the investigators or their designee(s). Research samples will be stored using BSI in accordance with NHLBI DIR Biospecimen policy. Data will be kept on the NHLBI P:drive, accessible through password-protected computers. Only the members of the research team will have access to the samples and data. Coded biospecimens may be sent to collaborators outside of the NIH with IRB approval in accordance with applicable NIH and DIR Policy for sharing research resources, including an executed material transfer agreement.

**Biospecimen Management at participating sites:**

Clinical samples will be tracked through the electronic medical records system. No research biospecimens will be collected at the WRNMMC study site.

**End of study procedures:**

Data retained by the NHBLI will be stored in a password-protected database in conformity with NHLBI DIR policy until they are no longer of scientific value.

Destruction of research data collected on this protocol will be consistent with NIH policy and upon permission of the Clinical Director.

**Breach of Confidentiality:**

PIs will report any breach of subject confidentiality or trial data to the clinical director and IRB per NIH policy, including NIH HRPP SOP 16 - Reporting Requirements for Unanticipated Problems, Adverse Events and Protocol Deviations.

### **Data Sharing and Future Use of Data**

#### **Data Sharing Plans:**

Research data may be shared with qualified non-collaborator recipients following publication of the primary research results after removal of PII and IRB approval (coded data) or Office of Human Subjects Research Protections (OHSRP) approval (unlinked data). In both situations, a data use agreement between the sender and the recipient will be executed. Future research use of data not defined in the research protocol may occur only after IRB review and approval or a determination from the NIH OHSRP. Refusal of a research subject participant to permit future use of data-will be honored.

#### **Future Use of Biospecimens:**

Following analyses of biospecimens for primary research purposes as described in the protocol, remaining samples suitable for future research will be stored in manner that conforms with DIR policy (such as BSI) or in a publicly accessible research biospecimen repository following IRB approval. Biospecimens may be destroyed only when permitted by the clinical director and approved by the IRB. Any future research use of biospecimens not defined in the research protocol will occur only after IRB review and approval, if the research holds the key that identifies research subjects, or determination from OHSRP (non-collaborative research). Biospecimens will not be sent outside of the NIH for future research use without IRB approval and an executed agreement. Refusal of a research subject participant to allow for future use of biospecimens will be honored.

**Loss or destruction of samples:** Should we become aware that a major breech in our plan for tracking and storage of samples has occurred, the IRB will be notified.

## **8. Statistical Considerations**

#### ***Primary study outcome:***

Continuous data will be presented as mean  $\pm$  standard deviation or median and range, as appropriate. The primary outcome of this pilot study will be the comparison of baseline to 12-week (on NR) skeletal muscle fixed-load sub-maximal exercise NMR spectroscopy skeletal muscle phosphocreatine recovery time. We are proposing a novel study with no data available on the effect of NR on mitochondrial function as measured in-vivo as measured by NMR spectroscopy. However, we appeal to data in Wang, et. al (ref. 20) to aid with a preliminary sample size calculation. In the Wang, et. al. study, the mean recovery time in leg muscle

phosphocreatine levels after foot-exercise in the control group was  $36.7 \pm 6.6$  seconds. Based on the paired t-test, a sample of size 15 will allow our study to detect a 13% or greater relative reduction (4.8 sec or greater absolute reduction from 36.7 sec to 31.9 sec) in skeletal muscle recovery time with NR at 12 weeks compared to baseline with 80% power and a two-sided alpha of 0.05. The calculation assumes that the standard deviation of the recovery times of the paired baseline to 12-week differences on NR is the same as the standard deviation of the phosphocreatine recovery times in the control group (i.e. 6.6 sec) of the Wang, et. al. study. We request the enrollment of 20 subjects to allow for subject attrition and a margin of error for the study assumptions. The primary analysis of the primary endpoint will use a non-parametric Wilcoxon Signed Rank test for paired data.

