## **2. Objectives**

A pilot study will be undertaken where up to 25 participants with clinically stable, systolic heart failure (LVEF  $\leq 45\%$ ) will be enrolled with a goal of having 15 subjects complete the treatment. NR will be increased at two weekly intervals by 250 mg/dose (500 mg/day) to a final dose of 1000mg PO BID (2000 mg/day). Clinic visits with bi-weekly labs during dose escalation will assess HF symptoms and monitor proBNP, CBC, HbA1C, ALT, CK, insulin/glucose, uric acid, electrolytes, BUN/Cr levels. Serum NAD+ levels will be measured at baseline, 12 and 16 weeks and baseline (within 3 months of enrollment) and 12 week echocardiograms will be performed to measure left ventricular systolic and diastolic function.

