#### **Description of Study Population and Recruitment**

The WRNMMC has an active heart failure clinic where approximately 500 ambulatory heart failure patients are seen on a regular basis. The Cardiologists staffing the clinic review all heart failure patients the day prior to their appointments and they determine who potentially meets inclusion and exclusion criteria for studies. The patients who are eligible are then informed about the study at their appointments and asked whether they would be willing to be screened, consented and enroll in the studies.

We will also recruit subjects through NIH using traditional recruitment methods such as referrals from other protocols, outside physician referral and self-referral.

The study may also opt to use the following strategies for recruitment of patients :

- ClinicalTrials.gov
- Clinical Center Research Studies website
- National Heart, Lung and Blood Institute (NHLBI) patient recruitment website
- Twitter messages and chats with study investigators
- Social Media posts
- Use of CC Office of Patient Recruitment services including creation and distribution of study flyers and information through pre-existing recruitment avenues such as the NIH recruitment listserv.

Up to 25 participants may be recruited for this study with the objective of having 15 subjects completing the study.

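### The 80% power claimed for the paired t-test with 15 subjects is really about 75%, and about 72% for the planned Wilcoxon test if the differences are normal

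*Combined protocol and SAP*

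**What the plan says.** Section 8 (Primary study outcome) makes the power claim: "Based on the paired t-test, a sample of size 15 will allow our study to detect a 13% or greater relative reduction", which it also expresses as a "4.8 sec or greater absolute reduction from 36.7 sec to 31.9 sec". It attaches 80% power and a two-sided alpha of 0.05. The standard deviation of the baseline to 12-week differences is taken to equal the 6.6 s seen across control subjects in a cited study.

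The same paragraph then names a different test for the analysis: "The primary analysis of the primary endpoint will use a non-parametric Wilcoxon Signed Rank test for paired data". No power is given for that test.

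On numbers, Section 8 says: "We request the enrollment of 20 subjects to allow for subject attrition and a margin of error for the study assumptions". Section 2 (Objectives) allows up to 25 participants, who "will be enrolled with a goal of having 15 subjects complete the treatment". The recruitment text in Section 3 agrees with Section 2: "Up to 25 participants may be recruited for this study with the objective of having 15 subjects completing the study". The face sheet lists 25.

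**The concern.** With only 15 pairs, the difference between a z calculation and a t calculation is not negligible. The variance is estimated on 14 degrees of freedom, so the two-sided 5% critical value is 2.145 and not 1.960. A calculation that uses 1.960 but is described as a paired t-test overstates the power. The planned Wilcoxon test loses a little more when the differences are normal.

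This is the only power statement in the plan, and it is tied to the number of completers the study sets as its goal. If the study meets that goal and finds nothing, a reader who relies on Section 8 will take the type II error at 4.8 s to be 20%. It is about 25% for the t-test and about 28% for the Wilcoxon test under normal differences.

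**Working it through.** **Inputs, all from Section 8:** n = 15 pairs; reduction 4.8 s from a mean of 36.7 s; standard deviation of the differences 6.6 s; two-sided alpha 0.05. The standardised effect is 4.8 / 6.6 = 0.727.

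**1. Reproducing the protocol's figure with the normal formula.**
- Required n = (1.960 + 0.842)² × (6.6 / 4.8)² = 14.84, rounded up to 15.
- Power at n = 15 = Φ(0.727 × √15 − 1.960) = Φ(2.817 − 1.960) = 80.4%.
- Detectable reduction at n = 15 = 2.8016 × 6.6 / √15 = 4.77 s, and 4.77 / 36.7 = 13.0%.

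These agree with the stated 15 subjects, 80%, 4.8 s and 13%. Section 8 does not give its formula, so its use of the z formula is an inference.

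**2. The test that Section 8 names for the calculation.** Power of the paired t-test comes from the noncentral t distribution with 14 degrees of freedom, noncentrality 0.727 × √15 = 2.817 and critical value 2.145. The result is **74.5%**. Two alternative readings do not recover 80%:
- using the unrounded 13% (0.13 × 36.7 = 4.77 s) gives 74.0%;
- a one-sided test gives 84.9%.

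**3. The test planned for the analysis.** At n = 15 the exact two-sided signed-rank test rejects when the smaller rank sum is 25 or less (attained level 0.0479). Power was simulated with at least 400,000 trials per setting. Normal differences with mean 4.8 s and standard deviation 6.6 s give **about 72%**. The documents say nothing about the shape of the differences, so other shapes were tried with the same shift and standard deviation:

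| Shape of the differences | Wilcoxon power, n = 15 |
|---|---|
| Uniform | 66% |
| Normal | 72% |
| Logistic | 76% |
| t with 5 df | 79% |
| Laplace | 79% |

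**4. Completers needed for 80% at 4.8 s.** Wilcoxon figures assume normal differences.

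| Completers | Paired t-test | Wilcoxon |
|---|---|---|
| 15 | 74.5% | 72% |
| 16 | 77.6% | 74% |
| 17 | 80.4% | 77% |
| 18 | 82.8% | 81% |
| 20 | 87.0% | 85% |

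The t-test needs 17 and the Wilcoxon test 18. The losses this allows are:
- from 20 enrolled: 20 − 17 = 3 (t-test) or 20 − 18 = 2 (Wilcoxon);
- from 25 enrolled: 25 − 17 = 8 (t-test) or 25 − 18 = 7 (Wilcoxon).

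**5. Reduction detectable with 80% power at 15 completers.**
- t-test: 5.13 s, and 5.13 / 36.7 = 14.0%.
- Wilcoxon, normal differences: about 5.28 s, and 5.28 / 36.7 = 14.4%.

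**The case against.** The strongest reply is that this is a pilot with a self-described preliminary calculation, and that the borrowed standard deviation matters more than the choice between z and t. That is true. If the recovery times have a standard deviation of 6.6 s at both visits, a standard deviation of 6.6 s for the differences implies a within-subject correlation of 0.5. The documents give no correlation, so the following values are assumptions: t-test power at n = 15 is 67% at 0.4, 75% at 0.5, 83% at 0.6 and 92% at 0.7. A standard deviation of the differences of about 6.17 s would be enough to bring the t-test to 80%. But the borrowed standard deviation is a disclosed assumption, and the stated power is wrong even if it holds exactly.

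A second reply is that the enrolment margin absorbs the shortfall: the 20 requested are meant partly to cover error in the assumptions, and a ceiling of 25 leaves more room. Either could deliver 17 or 18 completers. Neither rescues the claim as written, because Section 8 attaches the 80% to 15 subjects and Sections 2 and 3 make 15 completers the goal.

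A third point stands in part. Section 8 claims no power for the Wilcoxon test, so the only error in a stated figure is the t-test gap of about 5.5 points. The 72% is conditional on normality, and heavier tails would raise it. Still, the plan leaves its own primary test without a power figure, and none of the shapes tried reached 80%.

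Finally, the mismatch between 20 and 25 is a separate inconsistency. It adds nothing to the power error and is raised here because the same paragraph must be edited.

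**Conclusion.** The concern holds. On Section 8's own inputs, the paired t-test with 15 subjects has 74.5% power, not 80%. The planned Wilcoxon test has about 72% under normal differences, some 8 points below the advertised figure. The shortfall is 2 completers for the t-test and 3 for the Wilcoxon test, or about 0.3 s and 0.5 s of detectable reduction.

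The t-test result rests only on the stated inputs and normal differences; the Wilcoxon result also depends on the shape of the differences. The size is modest. It does not touch type I error or the validity of the analysis, but it should be corrected because it is the plan's only power statement.

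**What to change.** Reword Section 8 so that the power matches the test and the number of completers:

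- For 15 completers and a 4.8 s reduction, state about 72% power for the Wilcoxon test, assuming normal differences, and 75% for the paired t-test.
- Give the reduction detectable with 80% power at 15 completers: about 5.3 s (14.4%) by Wilcoxon, or 5.1 s (14.0%) by t-test.
- State that 80% power for 4.8 s takes 18 completers by Wilcoxon or 17 by t-test.
- Use one enrolment number throughout: Section 8 says 20, the face sheet says 25, and Sections 2 and 3 say up to 25.

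The cost is a wording amendment and a slightly less favourable power statement. No patients are added and the analysis does not change.
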